6.0 Data Collection and Management

The study CRFs are the primary data collection instrument for the study. Participating clinical sites will be provided with the study CRFs prior to the initiation of local enrolment. All data requested on the CRFs must be recorded, and any missing data must be explained.

6.1 Data Transmission

6.1.1 Electronic Data Capture System – Trial Database

We will utilize the REDCap Cloud system as the PERFORM trial database. All data will be stored on the secure server with no data stored locally on the user's computer. Unauthorized access to the system is restricted by means of a firewall and data encryption protection applied to all communications and data transmissions. Regular system maintenance ensures security risks are minimized. The database will store clinical trial data entered by local site personnel from the PERFORM CRFs. Data will be organized according to trial visit. The preliminary visit schedule is as follows (with permissible visit windows if applicable):

- Screening,
- Baseline,
- 2-Week Follow-Up (1 – 3 weeks post-surgery),
- 6-Week Follow-Up (4 – 8 weeks post-surgery),
- 4-Month Follow-Up (3 – 5 months post-surgery),
- 6-Month Follow-Up (5 - 7 months post-surgery),
- 9-Month Follow-Up (8 - 11 months post-surgery), and
- 1-Year Follow-Up (\geq 12 months post-surgery).

6.1.2 Randomization System

The Randomize.Net randomization system requires internet access and can be used on any device that can connect to the internet (e.g., computer, tablet, smartphone). Randomize.Net is a comprehensive randomization service for clinical trials that allows clients to define features and customize them specific to their trial, including stratification, multiple treatments, block sizes, masking and participating clinical site identifiers (in order for the system to generate unique participant identifiers). Online support is available for questions regarding set-up, updates and problems using the system. The database will store the stratification trial data entered by local site personnel, as well as the treatment allocation and unique participant identifier generated by the randomization system.

6.2 Data Integrity

6.2.1 Data Transmission

Study personnel at each participating clinical site will submit the required data, as detailed on the CRFs, to the Methods Center using the RedCap EDC system. Study personnel at each participating clinical site will receive unique login credentials (username and password) for the EDC systems and will be able to view and modify data for participants recruited at their respective clinical site. Study personnel at each participating clinical site will receive a Study Resource Binder, which will include detailed instructions on using the REDCap EDC system.

6.2.2 Data Integrity

The REDCap EDC system uses a variety of mechanisms for checking data at the time of entry including skip logic, range checks and data type checks. Data cleaning procedures will also be performed on a regular basis. Upon receipt of new data, Methods Center personnel will query all missing, implausible, or inconsistent data. Study personnel will be able to review all open queries for their respective clinical site in the system and will be

required to promptly respond. The Study Resource Binder will include detailed instructions on addressing queries in the RedCap EDC system.

6.2.2 Data Preservation and Sharing

Upon the completion of the follow-up period for all trial participants, and only once all data cleaning activities have been completed, designated trial team members will be responsible for the notification to the Data Manager to remove access to the trial database for all local site personnel. Only the Data Manager, Research Manager, Research Assistant and Study Statistician will continue to have access to the trial database and randomization system. Once the data is extracted and primary analyses are completed and published, the trial team members will make the data available upon request to collaborators for secondary analyses.

7.0 Ethical Considerations

This study is to be conducted according to international standards of Good Clinical Practice, applicable government regulations, and institutional research policies and procedures. Both study arms fall within the spectrum of current standard practice, as do the standardized post-operative follow-up visits.

7.1 Research Ethics Approval

This study protocol will be submitted to a properly constituted independent ethics committee (such as a research ethics board [REB] or an institutional review board [IRB]), in agreement with local legal prescriptions, for formal approval of the study conduct. The Methods Center at McMaster University will receive ethics approval from the Hamilton Integrated Research Ethics Board (HiREB) prior to the distribution of this protocol and any approved study materials to participating clinical sites. At each participating clinical site, the decision of the appropriate local ethics committee concerning the conduct of the study will be made in writing to the local investigator. A copy of this decision will be provided to the Methods Center prior to the local commencement of this study.

7.2 Informed Consent Form

All patients eligible for this study will be provided with a Participant Information Sheet and Informed Consent Form describing this study and providing sufficient information for patients to make an informed decision about their participation in this study. The Informed Consent Form will comply with the Health Insurance Portability and Accountability Act, if applicable, and will be submitted with the study protocol for formal review and approval by the appropriate ethics committee. The formal consent of a study participant, using the ethics committee-approved Informed Consent Form, must be obtained prior to the subject undergoing any study procedure.

7.3 Confidentiality

Information about study participants will be kept confidential and managed in accordance with the following rules:

- All study-related information will be stored securely;
- All study participant information will be stored in locked file cabinets (for paper documents) and/or secure digital files, and accessible only to study personnel;
- All paper and electronic CRFs will be identified only by a coded participant ID number and initials; and
- All study databases will be password-protected.

The communication, transmission and storage of participant data will comply with the applicable ethics committee. In the event that a participant revokes authorization to collect or use personal health information, the participating clinical site retains the ability to use all information collected prior to the revocation of participant authorization. For participants who have revoked authorization to collect or use personal health information, attempts will be made to obtain permission to collect at least vital status at the end of their scheduled study period.

7.4 Protocol Amendments

Any amendments to the study protocol that may affect the conduct of the study or the potential safety of, or benefits to, participants (e.g., changes to the study objectives, study design, sample size, or study procedures) will require a formal amendment to the protocol. Any protocol amendments will be approved by the Principal Investigator, the HiREB, local ethics committees and funders (as needed). Participating clinical sites will also be required to submit amendment requests to their local ethics committees to obtain approval for the amendment, and to provide the Methods Center with a copy of this approval. Administrative changes (e.g., minor corrections or clarifications that have no effect on the way the study is conducted) will not need to undergo a formal amendment process.

7.5 Safety and Adverse Events

7.5.1 Definitions

7.5.1.1 Adverse Event

An adverse event (AE) is any symptom, sign, illness, or experience that develops or worsens in severity during the course of the study or can be related when there is a reasonable possibility that the event might have been caused by study participation.

7.5.1.2 Serious Adverse Event

Adverse events are classified as serious or non-serious. A serious adverse event (SAE) is any AE that is any of the following:

- Fatal;
- Life-threatening;
- Requires or prolongs hospital stay;
- Results in persistent or significant disability or incapacity;
- A congenital anomaly or birth defect; or
- An important medical event.

7.5.1.3 Unanticipated Problems Resulting in Risk to Participants or Others

Any incident, experience or outcome that meets all of the following criteria will be considered an unanticipated problem that results in risk to participants or others:

- Unexpected in nature, severity, or frequency
- Related or possibly related to participation in research (i.e., possibly related means there is reasonable possibility that the incident, experience, or outcome may have been caused by the procedures involved in the research); and
- Suggests that the research places participants or others at greater risk of harm (including physical, psychological, economic, or social harm).

Unanticipated problems resulting in risk to participants or others encompass more than what one usually thinks of as AEs. 'Problems involving risk' may not necessarily result in harm. For example, misplacing a participant's study records containing identifiable private information introduces the risk of breach of confidentiality. Confidentiality may or may not be breached, but either way, this would be a reportable event. Risks to others must also be reported. For example, an unexpected outburst during questionnaire administration by a study participant that put study personnel at risk would be a reportable event.

7.5.2 Clinical Site Reporting

Participating clinical sites are responsible for reporting related AEs and all SAEs (irrespective of the relatedness of the event to the study intervention) to the Methods Center immediately, as well as their local ethics committee in accordance with local reporting requirements. Unanticipated problems resulting in risk to participants or others are also to be promptly reported to the Methods Center and the appropriate ethics committee if required.

7.5.2.1 Notifying the Methods Center

Participating clinical sites are responsible for reporting related AEs and SAEs to the Methods Center via the Adverse Event Form in the REDCap Cloud database. The original Adverse Event Forms will be kept in the relevant participant's file. Significant new information on ongoing SAEs will also be promptly provided to the Methods Center via the REDCap Cloud system. Unanticipated problems resulting in risk to participants or others are also to be promptly reported to the Methods Center via telephone or email. Detailed instructions on reporting related AEs, SAEs or unanticipated problems resulting in risk to participants or others will be provided to study personnel at each participating clinical site in the Study Resource Binder.

7.5.2.2 Notifying the Appropriate Ethics Committee

Participating clinical sites are responsible for reporting SAEs and unanticipated problems resulting in risk to participants or others to their local ethics committee (such as an IRB or REB), or a central ethics committee, in accordance with local reporting requirements. Copies of each report and documentation of ethics committee notification and receipt will be kept in the participating clinical site's study file.

7.5.3 Participant Safety and Monitoring

7.5.3.1 Participant Risks and Benefits

Both surgical techniques and associated hardware are indicated and approved for use in MBD patients with impending or realized pathologic fractures of the proximal femur, and they are both commonly used across North America in this patient population. The typical risks of surgery, such as bleeding, infection, deep vein thrombosis and neurovascular injury, apply equally to participants irrespective of the trial arm. These are inherent risks within the operative procedures for the treatment of this condition. Additional risks associated with internal fixation include revision surgery as a result of implant failure or disease recurrence. Additional risks associated with resection and endoprosthetic reconstruction include a potential increased risk of a surgical site infection, given the complexity of the procedure and the more invasive nature of the procedure. Our trial's DSMB will closely monitor event reporting and, should a differential risk of benefits be identified, they will consider stopping the trial. As in any trial, there is a potential risk of a breach of confidentiality. However, our trial team has extensive experience in the management of sensitive patient information and all possible precautions will be taken to ensure the security of these data. We will also work with clinical site personnel to ensure confidentiality is upheld at clinical sites.

Studies show that surgical site infections are less common with internal fixation, only a few percent, compared to up to 10 percent with reconstruction, because it is less invasive, meaning it has smaller incisions. However, there is a concern that with this surgery there may be an issue with increased likelihood of recurrent disease, up to 15 or 20 percent, compared to almost none with reconstruction. In fact, reconstruction approaches can last longer, which is important as people live longer with metastatic bone disease. However, these surgeries are complicated, may take a bit longer to complete, and can be expensive. They also have a higher chance of complications, like hip dislocations (a few percent) after the surgery.

It is not clear at this time that one surgical technique will provide any benefit over another. However, all participants will receive treatment for their impending or realized pathologic fracture in a manner that is

considered acceptable and within the standard of care. They may also benefit from the additional observation provided, as well as trial personnel communication and patient-reported outcomes questionnaires.

7.5.3.2 Data and Safety Monitoring Board

As per the principles established by the Data Monitoring Committees: Lessons, Ethics, Statistics (DAMOCLES) Study Group charter, we will establish a DSMB prior to the commencement of the feasibility phase of the PERFORM trial to oversee the safety of the trial participants and the overall conduct of the trial. The PERFORM DSMB will consist of members who are independent of the trial, free of conflicts with any of the investigative team, and will include experts in orthopaedic oncology and biostatistics, as well as an independent patient representative. The membership and responsibilities of the PERFORM DSMB will be detailed in the PERFORM DSMB Charter. Briefly, the DSMB will review accumulated safety data (i.e., SAEs) from the trial reports and advise the Principal Investigators and trial team on items related to trial safety. The DSMB is responsible for safeguarding the interests of participants, assessing the safety and efficacy of trial procedures and monitoring the overall conduct of the trial.

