4.6 Data Collection and Participant Follow-Up

At baseline, we will collect pre-operative demographic and cancer-related data from various sources, including the participant or proxy, the participant's medical chart, and/or the participant's treating surgeon. The data will include details such as age, sex and gender, co-morbidities, life-expectancy based on surgeon estimate and pre-surgical functional status, and anatomic characteristics of the femoral metastatic lesion. Participants will also pre-operatively complete the PROM questionnaires. We will document surgical details, peri-operative care, and in-hospital data, including the timing of surgery and any co-interventions used that may mediate treatment effects (such as post-operative mobilization and therapy), as well as any serious adverse events (SAEs) that occurred during hospitalization. After discharge, participants will be followed for one year, during which they will be assessed by their treating surgeon at two and six weeks; four, six and nine months; and one-year post-surgery. At each visit, we will document physical therapy, ability to ambulate, re-operations, hospitalizations, and SAEs. PROM data will be collected at all visits; however, the burden is low due to the short nature of the questionnaire. The utility score from the PROPr: PROMIS®-Preference Scoring System will be collected at baseline and 6 and 12 months. Trial data will be securely stored in the trial database accessible only to authorized personnel. See **Table 4** below:

Table 4. Study Flow

CATEGORY	STEPS		DATA COLLECTED
Recruitment	Identification of Patients		
	Assessment of Patient Eligibility		Screening Data
	Informed Consent		Informed Consent Form
Pre-Operative (Baseline)	Pre-Operative (Baseline)		Demographics Cancer-related data PROMIS®-PROPr questionnaire PROMIS® Physical Function
	RANDOMIZATION 		
Follow Up Visits	Internal Fixation	Resection and Reconstruction	
	Peri-Operative	Peri-Operative	Surgical details Peri-operative care Serious Adverse Events (SAEs)
	2 Week	2 Week	Follow-Up Data Package: X-rays; PROMIS® Physical Function questionnaire; Demographics, health-related questions, Mortality Status; Patient-reported days at home; Recurrence of cancer; SAEs
	6 Week	6 Week	Follow-Up Data Package: X-rays; PROMIS® Physical Function questionnaire; Demographics, health-related questions, Mortality Status; Patient-reported days at home; Recurrence of cancer; SAEs

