4.7.2 Adjudication of Outcomes

The use of Central Adjudication Committees (CAC) in randomized controlled trials significantly increases data quality and reduces inaccuracies by minimizing biased outcome assessment and between-site variability. The membership and responsibilities of the PERFORM CAC will be detailed in the PERFORM CAC Charter. Briefly, the PERFORM CAC will be comprised of three orthopaedic oncologists, a medical oncologist and a radiation oncologist. Using pre-defined decision rules that will be documented in the PERFORM CAC Charter, the PERFORM CAC will adjudicate: 1) case eligibility; 2) unplanned re-operations; 3) local recurrence; 4) serious adverse events and 5) mortality (cause of death). The CAC will reach a consensus on all reviewed cases. All decisions made by the Committee will be final. We anticipate that the PERFORM CAC will meet quarterly to review trial events that require adjudication.

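### Infection and dislocation, the harms expected to be more frequent with reconstruction, are not named for collection or adjudication, and the DSMB's input is described as SAEs only

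*Protocol*

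**What the plan says.** **Expected harms.** Protocol 7.5.3.1 states that "surgical site infections are less common with internal fixation, only a few percent, compared to up to 10 percent with reconstruction", and puts hip dislocation after reconstruction at a few percent. Section 1.2.1 names the same two complications as the price of the more invasive operation. For internal fixation, 7.5.3.1 names revision surgery after implant failure or disease recurrence. The same section lists infection among the surgical risks that "apply equally to participants irrespective of the trial arm", before giving the unequal rates.

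**Collection.** Section 4.6 says: "At each visit, we will document physical therapy, ability to ambulate, re-operations, hospitalizations, and SAEs". The study-flow table adds X-rays, health-related questions, recurrence of cancer, days at home and SAEs at each follow-up visit.

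**Reporting.** Under 7.5.2, sites are "responsible for reporting related AEs and all SAEs (irrespective of the relatedness of the event to the study intervention"). Section 7.5.2.1 routes both kinds of event through the Adverse Event Form.

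**Adjudication.** Section 4.7.2 lists eligibility, unplanned re-operations, local recurrence, then "4) serious adverse events and 5) mortality (cause of death").

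**Monitoring.** Section 7.5.3.1 says: "Our trial's DSMB will closely monitor event reporting and, should a differential risk of benefits be identified, they will consider stopping the trial". Section 7.5.3.2 then says that "the DSMB will review accumulated safety data (i.e., SAEs) from the trial reports".

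**The concern.** The trial asks whether a more invasive operation is worth its cost to the patient, so the harms expected to be more frequent with that operation should be collected at least as carefully as those expected with the comparator. As written, the fixation harms have their own visit items and their own adjudication items. The reconstruction harms have neither and rely on general adverse event reporting. That reporting depends on classification by site staff, who cannot be blinded (4.7.3). The board asked to act on a differential risk is described as seeing only the serious part of what is reported.

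At stake are the completeness of the between-arm harm comparison and the DSMB's view of it. An event that was never recorded cannot be recovered at analysis.

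**Working it through.** **Step 1. Trace each named harm through the protocol.**

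| Harm (7.5.3.1) | Arm it is tied to | Own visit item (4.6, study-flow table) | Own adjudication item (4.7.2) |
|---|---|---|---|
| Disease recurrence | Internal fixation | Yes | Yes (local recurrence) |
| Revision surgery | Internal fixation | Yes (re-operations) | Yes (unplanned re-operations) |
| Surgical site infection | Reconstruction | No | No |
| Hip dislocation | Reconstruction | No | No |

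**Step 2. Ask which infections or dislocations are still caught.**

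- Admitted, or stay prolonged: serious by definition (7.5.1.2). Within adjudication and DSMB review.
- Re-operated: recorded at the visit and adjudicated as an unplanned re-operation.
- Neither, but judged an important medical event: an SAE, at the site's discretion.
- Neither, not serious, judged related: reported on the Adverse Event Form, so in the database. Not on the adjudication list and not in the DSMB's stated input.
- Neither, not serious, judged unrelated: no stated reporting route and no visit item that asks for it.

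The gap is the last two lines: events managed without admission or re-operation and not called serious.

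**Step 3. Illustrate the size.** The protocol does not plan this comparison and does not give the share of events that would be non-serious or missed. The figures below only show how few events the harm comparison rests on.

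Inputs:
- Enrolment (5.1): 300/(1 − 0.10) = 333.3, so 334, which reproduces the plan. With 1:1 allocation (4.4) that is 167 per arm.
- Infection (7.5.3.1): up to 10 percent with reconstruction, taken as 10%. A few percent with fixation, taken as 3% and varied from 2% to 5%. These readings are assumptions.
- Two-sided 5% level.

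Expected infections: 167 × 0.03 = 5.0 and 167 × 0.10 = 16.7.

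Power ≈ Φ(d/SE − 1.96), with SE = √{[p₁(1−p₁) + p₂(1−p₂)]/167}.

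- Full capture, 3% vs 10%: SE = √[(0.0291 + 0.0900)/167] = 0.0267; d/SE = 0.07/0.0267 = 2.62; power = Φ(0.66) ≈ 75%. A pooled variance under the null gives 74%.
- Half captured in both arms, 1.5% vs 5%: SE = √[(0.014775 + 0.0475)/167] = 0.0193; d/SE = 0.035/0.0193 = 1.81; power = Φ(−0.15) ≈ 44%.

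| Fixation rate assumed (vs 10%) | Expected cases | Power, full capture | Power, half captured in both arms |
|---|---|---|---|
| 2% | 3.3 vs 16.7 | 88% | 58% |
| 3% | 5.0 vs 16.7 | 75% | 44% |
| 4% | 6.7 vs 16.7 | 58% | 32% |
| 5% | 8.4 vs 16.7 | 41% | 22% |

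Equal loss in both arms leaves the ratio of rates unchanged but halves the absolute difference, here from 7 to 3.5 percentage points.

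**The case against.** **Other routes exist.** Hospitalizations and re-operations are separate visit items, X-rays are taken at each follow-up visit, and the adjudicators review unplanned re-operations in their own right. An admitted infection or dislocation is serious without any appeal to site discretion. Related non-serious AEs must be reported. This stands. A reader might infer that these harms are seen only if a site calls them serious, and the protocol does not support that. The gap is confined to events managed without admission or re-operation. A scheduled X-ray would not show a superficial infection or a dislocation already reduced.

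**Relatedness.** The AE definition in 7.5.1.1 refers to whether "there is a reasonable possibility that the event might have been caused by study participation". A reader might infer that a site could dismiss a wound infection because both operations are standard practice. The text does not support this: that wording is one of two alternative limbs of the definition, and 7.5.2 speaks of relatedness to the study intervention. Relatedness still remains a judgement by unblinded staff, and no visit item prompts it.

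**The primary outcome.** Days at home counts days without healthcare contact, from the patient's diary, so outpatient treatment of a complication would normally register. That stands, but the component records contact and not its cause, so it cannot give infection or dislocation rates by arm.

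**Direction of bias.** A reader might infer that the trial will under-count harms of reconstruction and lean toward showing no excess. The protocol gives no capture rates, and unblinded sites that expect more complications after reconstruction could equally over-report them there.

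**Documents not shown.** Sections 4.7.2 and 7.5.3.2 are summaries that defer to charters. The case report forms and the Study Resource Binder may hold further items. This is fair, and it is why the point concerns what the protocol states. Its own summary limits the DSMB's input to SAEs, and that should agree with 7.5.2 and 7.5.3.1 whatever the charter says.

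**Equal infection risk.** The contradiction is minor, since 7.5.3.1 itself goes on to name a potentially increased infection risk with reconstruction. Nothing ties these rates to the definition of unanticipated problems in 7.5.1.3.

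**Conclusion.** The point holds in a limited form. Infection and dislocation are named as the harms expected to be more frequent with reconstruction, but not for structured collection or adjudication, while the fixation harms are named for both. The stated DSMB input is narrower than what sites report, and narrower than its task under 7.5.3.1 calls for. The harm comparison can therefore be incomplete for non-serious events managed without admission or re-operation.

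The size and direction of any under-count cannot be computed from the protocol. The fall from about 75% to about 44% power is an illustration. It rests on reading the infection rates as 3% and 10%, on 167 analysed per arm, and on an assumed half capture in both arms. This is a worthwhile, inexpensive improvement and not a flaw that invalidates the design.

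**What to change.** 1. In 4.6 and the study-flow table, add yes/no items for surgical site infection and hip dislocation to the follow-up package at the existing visits, recorded regardless of seriousness or relatedness.
2. Add both events to the adjudication list in 4.7.2, and align the adjudication charter.
3. In 7.5.3.2, replace the SAE-only parenthesis with SAEs, related AEs and these named events by arm, so that it agrees with 7.5.2 and 7.5.3.1.
4. In 7.5.3.1, reconcile the sentence that infection risk is equal across arms with the unequal rates given later in the same section.

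**Cost.** A protocol amendment, two tick-box items on forms for visits already planned, and a modest number of extra adjudications. On the 3% and 10% readings, with dislocation also at 3% in the reconstruction arm, that is about 5.0 + 16.7 + 5.0 ≈ 27 events over the whole trial. Some of these would go to the committee anyway as SAEs or re-operations, and it already expects to meet quarterly. No visits, tests or staff are added.
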